10.4.3 Assessment of Expectedness

If the event is an AR, the evaluation of expectedness will be made based on knowledge of the reaction and the relevant product information documented in the SPC/IB.

The event may be classed as either:

Expected: the AR is consistent with the toxicity of the IMP listed in the SPC/IB.

Unexpected: the AR is not consistent with the toxicity in the SPC/IB.

10.4.4 Assessment of Severity

The Investigator will make an assessment of severity for each AE/SAE and record this on the CRF or SAE form according to one of the following categories:

Mild: an event that is easily tolerated by the participant, causing minimal discomfort and not interfering with every day activities.

Moderate: an event that is sufficiently discomforting to interfere with normal everyday activities.

Severe: an event that prevents normal everyday activities.

Note: the term 'severe', used to describe the intensity, should not be confused with 'serious' which is a regulatory definition based on participant/event outcome or action criteria. For

example, a headache may be severe but not serious, while a minor stroke is serious but may not be severe.

10.5 REPORTING OF AEs TO THE SPONSOR

Adverse events occurring during the trial that are observed by the investigator or reported by the participant should be recorded in the patient's medical records.

Only SAEs/SARs/SUSARs will be documented in the eCRF and reported expeditiously to the Sponsor as below.

10.6 REPORTING OF SAEs/SARs/SUSARs

Once the Investigator becomes aware that an SAE has occurred in a study participant, the information will be reported to the ACCORD Research Governance & QA Office **immediately or within 24 hours**. If the Investigator does not have all information regarding an SAE, they should not wait for this additional information before notifying ACCORD. The SAE report form can be updated when the additional information is received. The SAE report will be submitted simultaneously to the CI.

The SAE report will provide an assessment of causality and expectedness at the time of the initial report to ACCORD according to Sections 10.4.2, Assessment of Causality and 10.4.3, Assessment of Expectedness.

The SAE report will be submitted electronically to the ACCORD Research Governance & QA Office and the CI directly from the study database. If the database is inaccessible then a paper copy of the SAE form should be completed and be transmitted by fax to ACCORD on **[name]** or may be transmitted by hand to the office or submitted via email to [contact]. Only forms in a pdf format will be accepted by ACCORD via email.

Where missing information has not been sent to ACCORD after an initial report, ACCORD will contact the Investigator and request the missing information. The Investigator must respond to these requests in a timely manner.

All reports will be retained by the Investigator in the Investigator Site File (ISF).

10.7 REGULATORY REPORTING REQUIREMENTS

The ACCORD Research Governance & QA Office is responsible for Pharmacovigilance reporting on behalf of the co-sponsors (The University of Edinburgh and Lothian Health Board).

The ACCORD Research Governance & QA Office has a legal responsibility to notify the regulatory competent authority and relevant ethics committee (REC that approved the trial). Fatal or life threatening SUSARs will be reported no later than 7 calendar days and all other SUSARs will be reported no later than 15 calendar days after ACCORD is first aware of the reaction.

ACCORD, unless otherwise delegated, will inform Investigators at participating sites of all SUSARs and any other arising safety information.

ACCORD will be responsible for providing safety line listings and assistance; however, it is the responsibility of the Investigator to prepare the Development Safety Update Report. This annual report lists all SARs and SUSARs reported during that time period. The responsibility of submitting the Development Safety Update Report to the regulatory authority and RECs, lies with ACCORD.

10.8 CENTRAL BLINDED REVIEW OF SAEs

To ensure that collected safety data is reliable and robust, a central blinded assessor will evaluate all investigator-reported SAEs. This reviewer will have access to the web-based SAE form once this has been reported by the local investigator and submitted to ACCORD. The independent reviewer will assess the event diagnosis, expectedness of event and likely

causality, blinded to treatment allocation. If required, the reviewer will be able to request further information from the specific trial sites. The outcome of the central blinded review will be made available to local investigators for information. In case of discrepancies, the investigator's assessment as reported to ACCORD will comprise the definitive safety data for this trial and will be used for all analyses. Should an investigator change their assessment based on the outcome of the central blinded review, they will update the SAE record and submit a follow-up report to ACCORD.

10.9 FOLLOW UP PROCEDURES

After initially recording an AE or recording and reporting an SAE, the Investigator should make every effort to follow each event until a final outcome can be recorded or reported as necessary. Follow up information on an SAE will be reported to the ACCORD office.

If, after follow up, resolution of an event cannot be established, an explanation should be recorded on the CRF or AE log or additional information section of the SAE form. Adverse events will continue to be recorded for 1 month after the last dose of IMP.

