Patients will receive a telephone call at 1-2 weeks post randomisation into the study and again after 3-4 weeks, with intermediary phone calls as necessary, to ascertain that they have escalated the dose and have achieved the full dose or are established on a tolerated dose if not the full dose. Further follow up by site or central Trial staff will occur at six months (phone/post) and 12 months (obtain MRI, phone/post/in person).

Figure 2. Study flow diagram

The patient will return to hospital to collect their next prescription every three or six months and for an MRI at 12 months.

After the end of 52 weeks, the patients will reduce the tablets over about two weeks and then stop the medication (section 6.2). They will return any unused drug to their local hospital pharmacy for tablet counting and then destruction. They will complete participation in the study after a final phone call when they are off the medication.

Participants who stop IMP (e.g. through tolerability issues or for medical reasons) will remain in the trial in follow-up unless they withdraw consent for further participation in the trial. Patients may withdraw consent at any time, in the event of which the trial will not collect further data on that patient. Data already collected will be kept and included in the analysis unless participants specifically ask for their data not to be included. Study medication maybe withdrawn in line with SPC guidelines at any time by the investigator or treating physician if deemed advisable for medical reasons, but the patient will remain in follow-up unless they withdraw consent.

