Participants with an indication for or contraindication to one of the trial drugs may still be randomised to the other trial drug. If a participant allocated to both trial drugs develops a contraindication to one of the trial drugs after randomisation into the trial, then they should discontinue that drug but continue to take the other trial drug. If a patient has to discontinue either or both drugs, they should continue to be followed up in the trial as planned (unless they withdraw from the trial). Patients should remain in follow up until the end of the trial follow up period, even if they discontinue trial drug, unless they withdraw from the trial.

The study will be performed open label. Placebo tablets are not available and masking by encapsulation is too complicated and expensive. However, blinding of outcomes is important to obtain unbiased information about tolerability, safety and efficacy. As such, structured symptom questionnaires, ascertainment of clinical outcomes and MRI analysis will be collected by individuals blinded to treatment allocation.

Treatment Allocation: Participants randomised to start drug will be provided with their allocated drug/s after randomisation at the baseline visit, which they will start on the next day (i.e. day 1, week 1). In the event that there is any delay between receiving the trial tablets and starting the treatment, then the patient will receive a reminder telephone call shortly before the day that the medication should be commenced. The first day of treatment defines day 1, week 1.

Participants will be supplied with trial tablets from the hospital pharmacy to cover a maximum period of six months. Detailed dated instructions on dosing will be provided in the patient pack. The participant will be telephoned between the end of weeks 1 and 2 and between the end of weeks 3 and 4, and other times during drug introduction as necessary, as well as follow-up time points, to ensure they are taking the medication correctly.

Drugs will be provided in their packs as marketed and licensed (i.e unaltered) and dispensed by the participating hospital pharmacy under research protocols.

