54	Nil	Nil	Nil	Nil

Table 4: Patients randomised to neither Isosorbide Mononitrate or Cilostazol

Neither ISMN/Cilostazol Dosing Regime				
Day	Isosorbide Mononitrate		Cilostazol	
	Morning	Evening	Morning	Evening
1-4	Nil	Nil	Nil	Nil
5-8	Nil	Nil	Nil	Nil
9-12	Nil	Nil	Nil	Nil
13, 14	Nil	Nil	Nil	Nil
At end of study				
Week	Morning	Evening	Morning	Evening
53	Nil	Nil	Nil	Nil
54	Nil	Nil	Nil	Nil

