7.2 STUDY ASSESSMENTS

Study assessments are shown in **Table 5** below, and in **Figure 2**.

Table 5: Study Assessments

Assessment	Prior to Baseline	Visit 1 Baseline	Week 1-2 FU	Week 3-4 FU	6 month FU	12 month FU
Screening for eligibility and Consent ¹ ;	X^s					
Confirm and document ongoing consent		X^s				
Medical including drug history		X^s				
Assess MR or CT diagnostic scan and send a copy to Edinburgh		X^s				
Randomisation		X^s				
Haematology (full blood count) and Biochemistry (urea, electrolytes, creatinine) – most recent value obtained since time of index stroke is acceptable unless clinical reason to expect change		X^s				
Blood Pressure recorded		X^s				X^{s,*}
Cognitive test: document years of education; Montreal Cognitive Assessment (MOCA)		X^s				
Timed Trail Making Test B		X^s				X^{s,*}
Dispense trial medication ²		X^s			X^s	
Structured questionnaire: symptoms; medication history and IMP tablet adherence			X^s	X^s	X^c	X^c
Structured Q: recurrent vascular events, mRS, TICS, TMOCA, SIS, ZUNG					X^c	X^c
Obtain IQCODE (post/phone) from relative						X^c
Follow-up brain MRI						X^s
Health Economics data: EQ-5D-5L, EQ-VAS						X^c
Adverse event / con meds reporting as necessary			X^s	X^s	X^{s,c}	X^{s,c}

¹Consent will be obtained before the data collection procedures commence or randomisation is performed.

Randomisation occurs at the end of the baseline visit. ^{*}at 12 months in some centres only. ²Dispensing in 3-monthly intervals is allowed. ^sAssessment performed by local site team. ^cAssessment performed by blinded assessor who is part of the central trial team.

SIS=Stroke Impact Scale, TICS= Telephone Interview for Cognitive Status, TMOCA= telephone MOCA.

Medical history: Will be performed by the study researcher and will include details of incident stroke, past medical history, vascular risk factors, medication history and years of education.

Baseline brain MR (preferred wherever possible) or CT: To identify the index stroke or exclude other causes of symptoms, and assess the burden of SVD – this is the clinical scan with T2, FLAIR, T1, T2* and diffusion imaging or CT obtained soon after the presentation with stroke that shows either:

- a recent, relevant (in time and location) acute lacunar infarct,

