10.1 DEFINITIONS

Adverse events will only be recorded/reported after the participant has been randomised into the trial.

An **adverse event** (AE) is any untoward medical occurrence in a clinical trial participant which does not necessarily have a causal relationship with an investigational medicinal product (IMP).

An **adverse reaction** (AR) is any untoward and unintended response to an IMP which is related to any dose administered to that participant.

A **serious adverse event** (SAE), **serious adverse reaction** (SAR). Any AE or AR that at any dose:

- results in death of the clinical trial participant;
- is life threatening*;
- requires in-patient hospitalisation[^] or prolongation of existing hospitalisation;
- results in persistent or significant disability or incapacity;
- consists of a congenital anomaly or birth defect;
- results in any other significant medical event not meeting the criteria above.

*Life-threatening in the definition of an SAE or SAR refers to an event where the participant was at risk of death at the time of the event. It does not refer to an event which hypothetically might have caused death if it were more severe.

[^]Any hospitalisation that was planned prior to enrolment will not meet SAE criteria. Any hospitalisation that is planned post enrolment will not meet the SAE criteria unless it constitutes an untoward medical occurrence (e.g. cosmetic elective surgery, social and/or convenience admission, etc., will not count as SAEs).

A **suspected unexpected serious adverse reaction** (SUSAR) is any AR that is classified as serious and is suspected to be caused by the IMP, that it is not consistent with the information about the IMP in the Summary of Product Characteristics (SPC) or Investigators Brochure.

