10.2 IDENTIFYING AEs AND SAEs

Participants will be asked about the occurrence of AEs/SAEs at each visit during the study. Participants will also be encouraged to contact the local PI or Central Trial Office (ECTU) via the Trial Helpline if they experience a potential adverse event. Open-ended and non-leading verbal questioning of the participant will be used to enquire about AE/SAE occurrence. Participants will also be asked if they have been admitted to hospital, had any accidents, used any new medicines or changed concomitant medication regimens. If there is any doubt as to whether a clinical observation is an AE, the event will be recorded.

AEs and SAEs may also be identified via information from GPs, other hospital specialties, and support departments e.g. laboratories, using usual procedures

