2	XX	XX (X)	XX (X)	XX (X)	XX (X)	XX (X)	XX (X)	XX (X)	XX (X)	XX (X)
3	XX	XX (X)	XX (X)	XX (X)	XX (X)	XX (X)	XX (X)	XX (X)	XX (X)	XX (X)
4	XX	XX (X)	XX (X)	XX (X)	XX (X)	XX (X)	XX (X)	XX (X)	XX (X)	XX (X)
>=5	XX	XX (X)	XX (X)	XX (X)	XX (X)	XX (X)	XX (X)	XX (X)	XX (X)	XX (X)
Old brainstem/cerebellar infarcts	XX	XX (X)	XX (X)	XX (X)	XX (X)	XX (X)	XX (X)	XX (X)	XX (X)	XX (X)
Probable old haemorrhage	XX	XX (X)	XX (X)	XX (X)	XX (X)	XX (X)	XX (X)	XX (X)	XX (X)	XX (X)
Non-stroke lesions (%)										
Non-stroke lesion	XX	XX (X)	XX (X)	XX (X)	XX (X)	XX (X)	XX (X)	XX (X)	XX (X)	XX (X)
Classification of non-stroke (%)										
Cerebral tumour	XX	XX (X)	XX (X)	XX (X)	XX (X)	XX (X)	XX (X)	XX (X)	XX (X)	XX (X)
Aneurysm	XX	XX (X)	XX (X)	XX (X)	XX (X)	XX (X)	XX (X)	XX (X)	XX (X)	XX (X)
Vascular malformation	XX	XX (X)	XX (X)	XX (X)	XX (X)	XX (X)	XX (X)	XX (X)	XX (X)	XX (X)
Other non-stroke classification	XX	XX (X)	XX (X)	XX (X)	XX (X)	XX (X)	XX (X)	XX (X)	XX (X)	XX (X)

Table 6a. Serious adverse events for ISMN.

Data are number (%).

Number	All			Fatal		
	ISMN	No ISMN	Difference (p)	ISMN	No ISMN	Difference (p)
Treatment						
During	xx (xx.x)	xx (xx.x)	BLR	xx (xx.x)	xx (xx.x)	BLR
After	xx (xx.x)	xx (xx.x)	BLR			
Relationship						
Possibly	xx (xx.x)	xx (xx.x)	Ch sq	xx (xx.x)	xx (xx.x)	Ch sq
Probably	xx (xx.x)	xx (xx.x)	-	xx (xx.x)	xx (xx.x)	-
Definitely	xx (xx.x)	xx (xx.x)	-	xx (xx.x)	xx (xx.x)	-

Table 6b. Serious adverse events for cilostazol.

Data are number (%).

Number	All			Fatal		
	Cilostazol	No Cilostazol	Difference (p)	Cilostazol	No Cilostazol	Difference (p)
Treatment						
During	xx (xx.x)	xx (xx.x)	BLR	xx (xx.x)	xx (xx.x)	BLR
After	xx (xx.x)	xx (xx.x)	BLR	xx (xx.x)	xx (xx.x)	BLR
Relationship						
Possibly	xx (xx.x)	xx (xx.x)	Ch sq	xx (xx.x)	xx (xx.x)	Ch sq
Probably	xx (xx.x)	xx (xx.x)	-	xx (xx.x)	xx (xx.x)	-
Definitely	xx (xx.x)	xx (xx.x)	-	xx (xx.x)	xx (xx.x)	-

Table 6c. Serious adverse events for combined ISMN and cilostazol.

Data are number (%).

Number	All			Fatal		
	ISMN /cil	No ISMN/cil	Difference (p)	ISMN /cil	No ISMN/cil	Difference (p)
Treatment						
During	xx (xx.x)	xx (xx.x)	BLR	xx (xx.x)	xx (xx.x)	BLR
After	xx (xx.x)	xx (xx.x)	BLR	xx (xx.x)	xx (xx.x)	BLR
Relationship						
Possibly	xx (xx.x)	xx (xx.x)	Ch sq	xx (xx.x)	xx (xx.x)	Ch sq
Probably	xx (xx.x)	xx (xx.x)	-	xx (xx.x)	xx (xx.x)	-
Definitely	xx (xx.x)	xx (xx.x)	-	xx (xx.x)	xx (xx.x)	-

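### The end of adverse-event recording is tied to the last IMP dose, so it is undefined for participants allocated no drug, and the SAP's SAE tables compare arms without a common observation window

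*Protocol*

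**What the plan says.** **Start and end of recording.** Protocol 10.1 starts the clock at randomisation in every arm: "Adverse events will only be recorded/reported after the participant has been randomised into the trial". The only sentence that ends it is in 10.9: "Adverse events will continue to be recorded for 1 month after the last dose of IMP". The group in Table 4 of section 6.2, "Patients randomised to neither Isosorbide Mononitrate or Cilostazol", takes no IMP and so has no last dose.

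**Follow-up after stopping.** Section 5.5.1 states: "Patients should remain in follow up until the end of the trial follow up period, even if they discontinue trial drug" (unless they withdraw). Section 3 says that those who stop IMP "will remain in the trial in follow-up unless they withdraw consent for further participation in the trial", and section 5.5.3 agrees. Section 10.2 adds: "Participants will be asked about the occurrence of AEs/SAEs at each visit during the study". Table 5 in section 7.2 has a row, "Adverse event / con meds reporting as necessary", marked at weeks 1-2, weeks 3-4, month 6 and month 12 with no on-drug restriction; SAP Table C repeats it. Section 10.6 requires an SAE report once the investigator learns of the event, with no reference to IMP status.

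**SAP.** Section 30 sends harms to Tables 6a-c and 7a-c. Table 6a ("Serious adverse events for ISMN") and its companions 6b and 6c have rows for SAEs during and after treatment, set against the no-drug group with logistic regression in the comparison column. Tables 7a-c count participants with at least one SAE. None states an observation window or uses person-time. The safety population in section 20 requires at least one dose.

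**The concern.** A count of participants with at least one SAE is comparable between arms only if the arms are observed for the same time. Here the one stated end point depends on treatment status, which differs by arm, and the trial is open label with site staff sharing AE reporting at months 6 and 12. A site that applied 10.9 literally would close the record of a participant who stopped all drug at month 2 at month 3, while a participant in the neither group has no stated end.

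The SAP does not repair this. The periods during and after treatment do not exist for someone never treated, so the Table 6 comparison has no defined comparator period. Protocol 9.1 names tolerability and safety as the main purposes of the trial, so an artefact in these tables bears on what the trial is for.

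**Working it through.** The documents give no figure for AE observation time, so there is nothing of theirs to reproduce. The check sets out what each reading of 10.9 implies.

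**Inputs from the documents**
- Recording ends 1 month after the last IMP dose (10.9).
- Treatment lasts 52 weeks, with reduced doses in week 53 and none in week 54 (6.2). A completer's last dose is therefore at the end of week 53.
- Tolerability target: fewer than 25% stop completely (2.2.2).
- Last scheduled assessment at 12 months (Table 5).

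**Assumptions not in the documents**
- Share stopping all IMP, f: 25% as the main case (the tolerability ceiling), range 10% to 40%.
- Month of stopping, t: 1, 3 or 6.
- Neither group observed for 12 months, since its scheduled contact ends there.

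**Formula.** Mean drug-group window W = (1 − f) × C + f × (t + 1) months, where C is the completer's window: 12 if capped, or 53 × 7 / 30.4375 + 1 = 13.19 if not. The ratio for both versus neither is W / 12.

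**Literal reading, capped at 12 months, f = 25%**

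| Stop month | W | Both v neither | Single-drug margin |
|---|---|---|---|
| 1 | 0.75 × 12 + 0.25 × 2 = 9.50 | 0.792 | 9.50 / 10.75 = 0.884 |
| 3 | 0.75 × 12 + 0.25 × 4 = 10.00 | 0.833 | 10.00 / 11.00 = 0.909 |
| 6 | 0.75 × 12 + 0.25 × 7 = 10.75 | 0.896 | 10.75 / 11.375 = 0.945 |

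The margin is milder because about half of the no-ISMN (or no-cilostazol) group takes the other drug and has its own last-dose clock. Its mean window is (W + 12) / 2. Over f = 10% to 40%, both versus neither runs from 0.96 to 0.67.

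**Literal reading, uncapped (C = 13.19)**
- f = 25%: W = 10.39, 10.89, 11.64; both versus neither 0.87, 0.91, 0.97.
- f = 10%: W = 12.07, 12.27, 12.57; ratio 1.01, 1.02, 1.05. The direction reverses.

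**Effect on an SAE proportion.** Assume equal true 1-year risk R and a constant hazard λ = −ln(1 − R) / 12. The recorded proportion in the drug group is (1 − f) × R + f × (1 − exp(−λ(t + 1))). For both versus neither, capped, f = 25%, the apparent risk ratio at t = 1, 3, 6 is 0.794, 0.836, 0.899 for R = 10% and 0.796, 0.840, 0.903 for R = 20%.

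**Extension reading.** If 10.9 only carries recording past the taper, every arm has at least 12 months, and drug completers have up to 13.19 − 12 = about 1.2 months more.

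**One common window.** The ratio is 1.00 in every comparison.

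**The case against.** The strongest reply is that 10.9 lengthens recording and does not shorten it. It speaks of recording continuing beyond the last dose, which fits the week-53 taper. Sections 3, 5.5.1 and 5.5.3 keep stoppers in follow-up, 10.2 and Table 5 ask about AEs throughout, 10.6 makes any SAE in a participant reportable, and the after-treatment rows in SAP Table 6 expect post-treatment events. This is persuasive. A reader might infer that the plan definitely cuts off early stoppers; the documents do not establish that, because early closure is one of two readings and no text says which governs.

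Three other stronger readings also fail:
- That recording in the no-drug groups never closes. The end is unstated, and scheduled contact stops at 12 months.
- That 0.79 to 0.90 describes all the SAE tables. It belongs to both versus neither (Tables 6c and 7c), capped, at 25% stopping. Moreover, a participant on both drugs who stops one should continue the other (5.5.1), so the clock still runs.
- That the drugs must look safer. Harm that leads to stopping occurs before the stop, and the next month is recorded too, so what is lost is mainly later, off-drug time. Bleeding, falls, heart attack and stroke or TIA are outcome events entered in the eCRF (10.3.2), blinded central assessors collect symptoms and vascular events at 6 and 12 months, and death is analysed as time to event (9.2).

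What the reply leaves standing: neither reading gives participants allocated no drug an end date, neither gives all arms the same window, and the SAP compares treatment-defined periods with people who had no treatment.

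**Conclusion.** The point holds as a conflict between passages and an undefined comparator window, not as a demonstrated bias. Section 10.9 ends AE recording by reference to a dose that some participants never take, can be read against the follow-up text, and feeds SAE comparisons that fix no window.

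The possible distortion ranges from a clear shortfall in drug-group observation, through nothing, to a small excess. It depends on which reading sites applied, how many stopped all IMP and when, and whether events after 12 months are counted. The stopping shares, stopping times and SAE risks used above are assumptions. The change is worth making because safety is a main purpose of the trial and 12-month follow-up already exists in every arm.

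**What to change.** - **Protocol 10.9.** Reconcile it with sections 3, 5.5.1, 5.5.3, 7.2, 10.2 and 10.6 by stating that AEs and SAEs are recorded in every arm from randomisation to the 12-month follow-up, whatever the IMP status.
- **SAP section 30 and Tables 6-7.** Base between-arm comparisons on that window for all randomised participants, and say expressly that those allocated no drug are included, since the section 20 safety set read literally omits them.
- **During/after rows.** Keep them, and any events after 12 months, as description for treated participants only. This preserves the on- and off-treatment information without a test against an undefined period.

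A common window running to month 13 would be less practical: the neither group has no scheduled contact after 12 months, so it would need a new one.

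The cost is a few more AE records for stoppers and small table changes. If collection is already complete, the SAP change can still be made before database lock, with a check that stoppers' AE records ran to 12 months.
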